## 5.1 Inclusion criteria

- 1) Patients aged  $\geq 18$  years ( $\geq 20$  years in Taiwan) at the time of informed consent
- 2) Patients who meet the 1987 revised ACR criteria or 2010 ACR/EULAR criteria

- 3) Patients who have RA within 2 years from initial diagnosis to informed consent
- 4) Patients who were previously untreated with MTX, JAK inhibitor, or bDMARDs
- 5) Patients who have disease activity of SDAI >11 at screening
- 6) Patients who are no need for concomitant use of DMARDs other than study drugs and hydroxychloroquine (only in South Korea and Taiwan) during the study as judged by principal investigator/sub-investigator at screening
- Patients who are no need for concomitant use of corticoid steroid equivalent to >10 mg/day prednisolone during the study as judged by principal investigator/subinvestigator at screening.
- 8) Female of child-bearing potential who can use appropriate contraceptive during the study, female in whom time from menopause to informed consent is ≥1 year, or female of no child-bearing potential through sterilization (bilateral tubal ligation, bilateral ovariectomy or hysterectomy, etc.)
- 9) Virile male who can use appropriate contraceptive during the study
- 10) Patients who can adequately understand this study procedures, and voluntarily consent in writing to take part in this study
   (consent of a legally-acceptable representative is also required for patients aged <20 years in Japan and aged <19 years in South Korea)

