## 7.2.6 ACR 20, 50, 70 response rates, and ACR-N

ACR 20 response is defined as a subject meeting all of the following 3 criteria based on the evaluation results of tender joint count, swollen joint count, VAS (physician- and patient-reported), HAQ, and CRP. Also, the proportion of ACR 20 response will be referred to as ACR 20 response rate.

- ≥20% improvement in the tender joint count (of the total 68 joints) compared to Week 0 of treatment
- ≥20% improvement in the swollen joint count (of the total 66 joints) compared to Week 0 of treatment
- ≥20% improvement in ≥3 of 5 parameters (physician- and patient-reported disease activities, patient-reported pain score, HAQ, and CRP) compared to Week 0 of treatment

ACR 50 response, ACR 50 response rate, ACR 70 response, and ACR 70 response rate are defined by the standards that 20% improvement of ACR 20 response and ACR 20 response rate is replaced to 50% and 70% improvement, respectively.

Also, ACR-N will be the lowest improvement rate among the following 3 parameters:

- Improvement rate of the tender joint count (of the total 68 joints) compared to Week 0 of treatment
- Improvement rate of the swollen joint count (of the total 66 joints) compared to Week 0 of treatment
- The 3rd highest improvement rate among the 5 parameters (physician- and patient-reported disease activities, patient-reported pain score, HAQ, and CRP) compared to Week 0 of treatment

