2.3. Handling of Study Data

- · Fixed data after the completion of follow-up will be used for statistical analyses.
- For subjects who were enrolled more than once, statistical analyses will be conducted by removing the data that became unnecessary.
- Data handling meeting will be held prior to the database lock to discuss and determine how to handle individual data after removing the information on which treatment arm each subject was randomized to.
- For clinical laboratory values that exceed or fall below detection limits, detection limits will be substituted for actual values.
- As a rule, baseline is defined as Week 0. If the value at Week 0 is missing or not measured, the time of screening is regarded as baseline.
- · Change and percentage change are defined as follows:

Change = measured value after intervention – measured value at baseline Percentage change = (change/measured value at baseline) x 100 (%)

- 2.4. Handling of Missing Values
 - Subjects with missing data at an assessment time point of SDAI remission, ACR20, ACR50, and ACR70 response, HAQ remission, and structural remission due to study discontinuation or other relevant reasons will be considered as a "non-responder" at the time point of missing data.
 - Subjects with missing data at an assessment time point of CDAI, DAS28-ESR, DAS28-CRP remission due to study discontinuation or other relevant reasons will be considered as a "non-responder" at the time point of missing data.
 - Any missing data on SDAI, CDAI, DAS28-ESR, and DAS28-CRP will be considered as missing at the time point of missing data.

If there is a missing data on the assessment of SDAI, CDAI, DAS28-ESR, DAS28-CRP, and mTSS, the sensitivity analysis of GEE or MMRM method will be performed. If the result does not converge, a missing data will be imputed with the last observation carried forward (LOCF). In addition, for the sensitivity analysis of primary endpoint, a missing data on the final scheduled visit will be imputed with data on End of Study.

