6.1. Analysis Plan of Primary Endpoint

The primary analysis for this study is intended to demonstrate the non-inferiority of ADA/MTX-reduced dose group (ARM-3) to ADA/MTX-MTD group (ARM-2) in terms of the primary endpoint, that is, SDAI remission rate at Week 48. The adjusted intergroup risk difference and its two-tailed 90% confidence interval in terms of SDAI remission rate at Week 48 will be calculated by Mantel-Haenszel test with country as a stratification factor to verify non-inferiority of ARM-3 to ARM-2 with the non-inferiority margin of -15%. As a sensitivity analysis, point estimates and their 95% confidence interval for changes in SDAI remission rate from baseline to each assessment timepoint will be calculated by generalized linear mixed model (Breslow NE, Clayton DG, J Am Stat Assoc 1993;88(421): 9-25, Wolfinger RD, O'Connell MA, J Stat Comput Sim 1993; 48: 233-243.). Unstructured

will be selected as a correlation structure, and if the analysis does not converge, Toeplitz, Autoregressive, Compound-symmetry structure will be used in order.

In addition, a missing data on the final scheduled visit will be imputed with data on End of Study to assess SDAI remission rate.

Furthermore, multiple logistic regression analysis will be conducted to assess potential effects of each explanatory variable on the response variable with SDAI remission/non-remission at Week 48 as the response variable, and age, sex, autoantibody profile, SDAI score at screening, change in mTSS from screening to Week 24 as explanatory variables, for which a model to minimize the AIC is to be adopted in principle by choosing appropriate variables.

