6.2. Analysis Plan of Secondary Endpoints

6.2.1. SDAI remission rate at Week 24

SDAI remission rate at Week 24 and its two-tailed 95% confidence interval will be calculated for each ARM (ARM-1, 2, and 3).

6.2.2. SDAI remission rate at Week 48 in MTX monotherapy groupSDAI remission rate at Week 48 and its two-tailed 95% confidence interval in MTXMonotherapy Group (ARM-1) will be calculated.

6.2.3. ACR20, ACR50, and ACR70 response rate at each assessment timepoint ACR20, ACR50, and ACR70 response rates and their two-tailed 95% confidence interval at each assessment timepoint will be calculated for each ARM (ARM-1, 2, and 3). Furthermore, Mantel-Haenszel test (risk difference) with country as a stratification factor will be performed to compare response rates at Week 48 between ARM-2 and ARM-3, and calculate the estimate of difference between the treatment arms and its two-tailed 95% confidence interval.

As a sensitivity analysis, point estimates and their 95% confidence interval for changes in ACR20, ACR50, and ACR70 response rates from baseline to each assessment timepoint will be calculated by generalized linear mixed model (Breslow NE, Clayton DG, J Am Stat Assoc 1993;88(421): 9-25, Wolfinger RD, O'Connell MA, J Stat Comput Sim 1993; 48: 233-243.). Unstructured will be selected as a correlation structure, and if the analysis does not converge, Toeplitz, Autoregressive, Compound-symmetry structure will be used in order.

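### The mixed-model sensitivity analyses in SAP 6.1 and 6.2.3 target change from a zero or near-zero baseline rate, so they do not check the Week 48 comparison of ARM-3 with ARM-2

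*SAP*

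**What the plan says.** SAP 6.1 sets the primary analysis as a country-stratified Mantel-Haenszel risk difference at Week 48 with a 90% interval against -15%. It then adds a sensitivity analysis: estimates and 95% intervals "for changes in SDAI remission rate from baseline to each assessment timepoint will be calculated by generalized linear mixed model". SAP 6.2.3 repeats this for "changes in ACR20, ACR50, and ACR70 response rates from baseline to each assessment timepoint will be calculated by generalized linear mixed model". Neither section states the link, the fixed effects, whether Week 0 is a modelled visit, or the reporting scale. The only rule for a failed fit in either section concerns the correlation structure: "if the analysis does not converge, Toeplitz, Autoregressive, Compound-symmetry structure will be used in order".

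SAP 2.3 fixes the reference point: "As a rule, baseline is defined as Week 0", and "If the value at Week 0 is missing or not measured, the time of screening is regarded as baseline".

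Three other provisions determine the rates at the early visits:

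- **ACR response (Protocol 7.2.6)** is measured against Week 0. One component is a required percentage "improvement in the tender joint count (of the total 68 joints) compared to Week 0 of treatment".
- **Entry (Protocol 5.1)** requires "Patients who have disease activity of SDAI >11 at screening". Remission is SDAI 3.3 or below (Protocol 7.2.4).
- **Randomisation (Protocol 4.3.1)** to ARM-2 or ARM-3 is only for subjects not in SDAI remission at Week 24. The mFAS contains only these two arms (SAP 3.1.1).

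**The concern.** A change from baseline in a response rate is informative only if the baseline rate can vary. Here it is fixed at zero for ACR and is at or near zero for SDAI remission. On the logit scale, zero responders at a visit means log-odds of minus infinity, and every contrast with that visit is infinite. Changing the correlation structure alters how a subject's visits are linked. It does not put a responder into an empty cell.

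The target is also the wrong one. Non-inferiority turns on the difference between ARM-3 and ARM-2 at Week 48, and 6.1 does not ask the mixed model for that difference. The other regression in 6.1, the multiple logistic model, does not list arm among its explanatory variables. This mixed model is therefore the only model-based sensitivity analysis attached to the primary arm comparison, and as worded it does not address that comparison.

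**Working it through.** The documents give no figure for this model, so there is none to reproduce. The check asks what the requested quantity is and whether it can be estimated.

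**Inputs.** From the documents: 110 per arm and 30% remission at Week 48 (Protocol 9.4.1); visits at Weeks 0, 4, 8, 12, 24, 36 and 48 (Protocol 7.5); Week 0 as baseline (SAP 2.3). Assumed: a logit link, Week 0 as a categorical level of visit, and the rates at the remaining visits.

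**Step 1: which cells are empty.**

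| Outcome | Week 0 | Week 24, ARM-2 and ARM-3 |
|---|---|---|
| ACR20/50/70 | exactly 0%, by definition | not fixed |
| SDAI remission | at or near 0%; the SDAI threshold applies at screening, up to 8 weeks earlier | exactly 0%, by the randomisation rule |

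**Step 2: an empty cell on the logit scale.** Ignoring correlation, 220 subjects with no responders contribute -220 × ln(1 + e^η) to the log-likelihood, where η is the visit log-odds. This is -3.99 at η = -4, -0.010 at η = -10 and -0.0000005 at η = -20. It always rises as η falls, so there is no finite maximum.

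A random intercept does not change this. Profiling a random-intercept logistic model over η gave:

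| η | ACR-like data | SDAI-like data (Weeks 0 and 24 empty) |
|---|---|---|
| -4 | -776.16 | -326.74 |
| -10 | -768.04 | -311.39 |
| -20 | -768.014 | -311.331 |
| -30 | -768.014 | -311.331 |

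**Step 3: what software prints.** In a logistic fit with arms pooled at Week 0, the Week 0 log-odds was -11.6 (SE 13) after 10 iterations, -26.6 (SE about 24,000) after 25, and -36 to -38 (SE above 3 million) after 50. GEE fits of the same data gave:

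| Working correlation | ACR-like: Week 0 log-odds (SE) | SDAI-like: Week 0 log-odds (SE) |
|---|---|---|
| Unstructured | -27.6 (undefined) | -28.6 (undefined) |
| Autoregressive | -34.5 (undefined) | -36.6 (472,000) |
| Compound symmetry | -34.1 (undefined) | -35.7 (835,000) |
| Independence | -27.6 (4,190) | -28.6 (5,180) |

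Every GEE fit reported convergence, so the fallback sequence might never start. Toeplitz was not run, but the argument in Step 2 does not depend on the structure.

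**Step 4: if SDAI remission at Week 0 is not quite zero.** If each subject has a 0.1% to 1% chance of remission at Week 0 (assumption), the chance of at least one in 220 is 1 - 0.999^220 = 20% to 1 - 0.99^220 = 89%. With exactly one, against 66 of 220 at Week 48:

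- log odds ratio = ln(66/154) - ln(1/219) = 4.54
- SE = √(1/66 + 1/154 + 1/1 + 1/219) = 1.01, treating visits as independent
- odds ratio about 94, with 95% limits of about 13 and 680

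The estimate is finite, but it rests on one subject.

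**Step 5: the rate scale.** With 0% at baseline, the change equals the visit rate. At 30% of 220 it is 30.0 points, SE √(0.3 × 0.7/220) = 3.1, 95% limits 23.9 to 36.1. That adds nothing to the by-visit rate.

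**Step 6: what remains estimable.** In the simulated SDAI data, 37 of 110 and 33 of 110 were in remission at Week 48. With the empty visits kept, the arm log odds ratio was -0.168, which matches ln(33/77) - ln(37/73). Its SE by hand is √(1/33 + 1/77 + 1/37 + 1/73) = 0.29. A fit restricted to Weeks 36 and 48 gave standard errors of 0.25 to 0.37.

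**The case against.** The strongest reply is that the SAP never says logit, never says Week 0 is a model level, and speaks of change in a rate. On that scale the quantity is finite. The very large standard errors come from contrasts with an empty visit: recode the same fit with Week 48 as reference and the arm contrast is ordinary. This stands. A reader might infer that the whole model has no solution, but the documents and the calculation support that only for contrasts against the empty cells. The remaining complaint is that the requested quantity is either degenerate or redundant, depending on a scale the SAP leaves open, and that the useful contrast is not requested.

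Other tempting readings also go too far:

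- **That the entry criterion forces 0% SDAI remission at Week 0.** The threshold applies at screening, and no threshold applies at Week 0. The zeros that are structural are ACR at Week 0 and SDAI remission at Week 24.
- **That LOCF is what remains if this model fails.** The sentence "If the result does not converge, a missing data will be imputed with the last observation carried forward" in SAP 2.4 concerns the index scores and mTSS, not the binary endpoint. The End-of-Study imputation and the PPS analysis are separate checks and still work.
- **That the model is fitted to responses already set to non-response.** SAP 2.4 makes that substitution for the response endpoints, but 6.1 does not say which data the mixed model uses. The point is open and should be stated.

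It is also fair that fitting only Weeks 36 and 48 discards earlier data that could support a missing-at-random analysis. A Week 24 covariate recovers part of that information, not all of it.

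**Conclusion.** The point holds in this form. With a logit link and Week 0 as a level of visit, the change-from-baseline contrast has no finite estimate for ACR, and none or an unstable one for SDAI remission. The listed correlation fallbacks cannot cure this, and convergence may still be reported. On the rate scale the result repeats the visit rate. On either scale, the sensitivity analysis in 6.1 does not test the non-inferiority conclusion, because it does not request the ARM-3 minus ARM-2 difference, and its 95% interval is not the 90% interval used for the margin.

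The conclusion about ACR at Week 0 and SDAI at Week 24 rests on definitions and design. The near-zero SDAI rate at Week 0 is an expectation, and the simulated figures depend on assumed visit rates. The Mantel-Haenszel primary analysis is unaffected. HAQ remission (SAP 6.2.4) uses the same model but has no baseline fixed at zero by design, so this point does not extend to it. The plan should be changed here, but the defect does not threaten the primary result.

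**What to change.** In SAP 6.1, and in the arm comparison of 6.2.3, replace change from baseline with the ARM-3 minus ARM-2 difference at Week 48, and specify:

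- a logistic mixed model on the post-randomisation visits, Weeks 36 and 48, in ARM-2 and ARM-3;
- fixed effects for arm, visit, arm by visit and country, with the Week 24 value as a covariate (SDAI for remission; name the corresponding Week 24 measure for ACR);
- observed responses only, without non-responder imputation;
- a model-standardised risk difference, with a 90% interval read against -15% for SDAI remission and a 95% interval for ACR.

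Keep the by-visit rates as descriptive output.

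The cost is SAP wording and a smaller model. The downside is that subjects with no observed value at Week 36 or Week 48 do not contribute to this sensitivity model. They remain in the primary analysis as non-responders.

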## 9.2.1.1 Method of analysis for primary efficacy endpoint

The primary analysis for this study is intended to demonstrate the non-inferiority of ADA/MTX-Reduced Dose Group (ARM-3) to ADA/MTX-MTD Group (ARM-2) in terms of the primary endpoint, that is, SDAI remission rate at Week 48. The intergroup difference in the SDAI remission rate and its two-tailed 90% confidence interval will be calculated based on a stratified analysis with country as a factor in mFAS as the main statistical analysis set. The non-inferiority margin shall be -15%.

Moreover, a multivariate statistical analysis on the SDAI remission rate at Week 48 will be performed for the following variables; age, gender, autoantibody profile, SDAI at screening, and change in mTSS from screening to Week 24.

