## 9.4.1 Sample size selection

Assuming that the SDAI remission rate is 30% for both ARM-2 and ARM-3, and the noninferiority margin is -15%, the number of subjects required for the lower bound of a twotailed 90% confidence interval for the intergroup difference in SDAI remission rate to exceed the non-inferiority margin at 80% power of detection would be 220 subjects in total (110 in each group).

Past reports suggest that the remission rate of MTX monotherapy is about 15%. Also, it has been reported that about 10% of patients cannot continuously receive MTX  $\geq$ 10 mg/week (Atsumi T, et al. 2016: 75-83). Thus, in order to randomize 220 subjects between ARM-2 and ARM-3, 288 subjects need to be enrolled, and considering some dropouts, a sample size of 300 subjects was selected as the target number of subjects to be enrolled.

<Justification for the estimated SDAI remission rate in ADA/MTX-Reduced Dose Group (ARM-3)>

The estimated SDAI remission rate in ARM-3 was calculated in reference to the results of the MTX Monotherapy  $\rightarrow$  ADA+MTX Group in HOPEFUL 1 Study in which Japanese MTX naïve patients receiving ADA+MTX or MTX alone for 26 weeks, and then, all subjects receiving ADA+MTX for another 26 weeks (Takeuchi T, et al. 2014: 536-43). Since the maximum dosage of MTX in HOPEFUL 1 Study was 8 mg/week (6.6±0.8 mg/week: Mean±SD), the results cannot be directly extrapolated to this study in which the maximum dosage of MTX up to Week 24 will be 16 mg/week; yet, the results would be appropriate to use as a reference for the SDAI remission rate in ARM-3 in which the dosage of MTX will be reduced to 6 to 8 mg/week from Week 24 onward. ARM-3 is designed for patients who have not achieved to SDAI remission at Week 24; thus, assuming that the subjects with SDAI remission at Week 26 in HOPEFUL 1 Study (20 subjects = 163 subjects × 12%) remain to be remission at Week 52, the Week-52 SDAI remission rate among the subjects with SDAI non-remission at Week 26 was calculated to be 31.5% [45/143 subjects, that is (65 subjects - 20 subjects)/(163 subjects -20 subjects)]. Therefore, the SDAI remission rate in ARM-3 was assumed to be 30%.

<Justification for the estimated SDAI remission rate of  $\leq$ 3.3 in ARM-2 (ADA/MTX-MTD Group)>

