2.6. Significance and Confidence Levels

The analysis on non-inferiority will be performed with a two-tailed confidence interval of 90%. A two-tailed significance level of 5% with a two-tailed 95% confidence interval will be used for all other analyses unless specified otherwise.

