2.8. Multiplicity Adjustment

Multiplicity will not be adjusted in this study.

3. Statistical Analysis Set

- 3.1. Definition of Statistical Analysis Set
- 3.1.1. Full analysis set (FAS)

FAS is defined as a group of subjects who receive study drug (MTX) and have evaluable efficacy data at 1 or more time points following the administration of study drug (including subjects who discontinued the study before Week 24 as well as those randomized to ARM-1, 2 or 3).

Modified FAS (mFAS) is defined as a group of subjects who are randomized after Week 24, receive study drug (ADA), and have evaluable efficacy endpoint at 1 or more time points following the administration of study drug (only the subjects randomized to ARM-2 or 3).

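### The logistic model for Week 48 SDAI remission is meant to assess each of five variables, but AIC selection leaves dropped variables with no planned estimate and shows weak or null ones that survive with inflated odds ratios and uncorrected intervals

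*SAP*

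**What the plan says.** Protocol 9.2.1.1 states that "a multivariate statistical analysis on the SDAI remission rate at Week 48 will be performed for the following variables" and lists age, gender, autoantibody profile, screening SDAI and the change in mTSS from screening to Week 24. It names no model and no fitting rule.

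SAP 6.1 turns this into a logistic regression with the same list: "age, sex, autoantibody profile, SDAI score at screening, change in mTSS from screening to Week 24 as explanatory variables". The aim is "to assess potential effects of each explanatory variable on the response variable". The sentence then ends with the selection rule: "for which a model to minimize the AIC is to be adopted in principle by choosing appropriate variables".

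The SAP gives no interval rule specific to this model, so the general rule in SAP 2.6 applies: "A two-tailed significance level of 5% with a two-tailed 95% confidence interval will be used for all other analyses unless specified otherwise". SAP 2.8 adds: "Multiplicity will not be adjusted in this study". Neither document plans to report the full model, single-variable results or the dropped terms, and neither plans a bootstrap, shrinkage or other allowance for selection.

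**The concern.** The aim and the rule do not fit together. To assess each variable, an estimate and interval are needed for each variable, including those with little apparent effect. A minimum-AIC subset gives no estimate for what it leaves out. What it keeps has passed a data-dependent filter, and the ordinary interval takes no account of that filter.

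At stake is the list of predictors of remission on adalimumab plus methotrexate. A reader would see a short table from which some pre-specified variables are absent and in which the weaker survivors look stronger and better estimated than they are.

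**Working it through.** The documents give no figure for this model, so there is none to reproduce.

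**Inputs from the documents.** Protocol 9.4.1: 220 randomised, with 30% remission ("Assuming that the SDAI remission rate is 30% for both ARM-2 and ARM-3"). Five candidate variables and minimum AIC (SAP 6.1). Two-sided 95% intervals (SAP 2.6). Three countries as randomisation strata (Protocol 4.3.1).

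**Step 1: does the planned size force selection?** Expected remissions: 0.30 × 220 = 66. With one parameter per variable, 66 / 5 = 13.2 events per parameter. Selection is not forced.

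**Step 2: what AIC does to one variable with no effect.** AIC = −2 log L + 2k, so one extra parameter is kept when its likelihood-ratio chi-square exceeds 2.
- P(kept) = P(chi-square on 1 df > 2) = 0.157.
- P(p < 0.05 given kept) = 0.05 / 0.157 = 0.318.
- Coverage of the displayed 95% interval given kept = 1 − 0.318 = 0.682, about 68%.
- P(kept and p < 0.05) = 0.157 × 0.318 = 0.050.

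The last line shows that selection leaves the false-positive rate per variable at 5%. What falls is the coverage of the intervals that are displayed.

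**Step 3: simulation with five candidates.** n = 220, 30% remission, three continuous and two binary variables, all 32 subsets compared by AIC, 1500 trials per setting, correlation 0 or 0.3. The odds ratios (per SD if continuous, between levels if binary), variable types and correlations are assumptions, because the documents give none. Ranges below span both correlations.

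| True effect | Kept | Coverage when kept | Mean OR when kept* |
|---|---|---|---|
| All five null | 14–18% | 59–74% | – |
| 1.2, continuous | 42–46% | 88–93% | 1.38–1.44 |
| 1.3, binary | 25–35% | 84–90% | 1.77–2.20 |
| 1.5, continuous | 83–89% | 94–98% | 1.57–1.66 |
| 1.5, binary | 38–47% | 90–93% | 2.01–2.66 |

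*Exponential of the mean log odds ratio.

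The 1.2 and 1.3 rows come from one setting and the two 1.5 rows from another. All five variables were kept together in under 1% of trials with all-null or weak effects, and in 5% to 13% when every odds ratio was 1.5. At least one listed variable was therefore dropped in 87% to 100% of trials. In the full five-variable model, 95% intervals covered the truth 93% to 96% of the time in every setting. Monte Carlo error on coverage given kept is about 1 to 3 percentage points.

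**Step 4: false positives in the same runs.** With all variables null, multiply P(kept) by P(p < 0.05 given kept). At zero correlation this runs from 0.156 × 0.261 = 0.041 to 0.163 × 0.320 = 0.052; the full model gives 0.041 to 0.053 (one minus coverage). At correlation 0.3 it runs from 0.142 × 0.413 = 0.059 to 0.171 × 0.398 = 0.068; the full model gives 0.049 to 0.061. The largest difference for any variable is about one percentage point.

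**The case against.** AIC selection from a short, pre-specified candidate list is a recognised method, and choosing the method is what a SAP is for. The rule applies only in principle and does not forbid showing the full model. The analysis is supplementary. These points stand, and they limit the weight of the concern. They do not supply an estimate for a dropped variable. Selection is easiest to defend for building a prediction model, but the SAP states no prediction aim and plans no validation.

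A reader might also draw stronger conclusions that the documents and arithmetic do not support:
- **That AIC produces too many false positives.** Setting the 32% of kept null variables that show p < 0.05 against 5% in the full model compares a conditional rate with an unconditional one. Looking only at full-model variables with p < 0.157 also gives about 30% to 35%. Like for like, the rates are about equal (Step 4).
- **That every displayed interval is too optimistic.** The loss of coverage is marked for null and weak effects. For continuous variables at an odds ratio of 1.5 per SD it is essentially absent.
- **That dropped variables will never be reported.** The accurate statement is that no report of them is planned.
- **That the SAP contradicts the protocol.** Protocol 9.2.1.1 fixes no fitting rule, and all five variables remain candidates.

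Events per parameter deserve a caution. Adding country takes two terms, giving 7 parameters and 66 / 7 = 9.4 events each. If autoantibody profile takes two terms, that becomes 66 / 8 = 8.3. This is thinner than 13.2 but still workable.

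**Conclusion.** The mismatch between aim and method holds, and it is minor. Under the SAP as written, one or more of the five variables will very likely have no planned estimate. A null single-parameter variable is kept about 16% of the time, with about 68% coverage when kept. Weak effects are exaggerated when kept, with a true 1.2 per SD shown as about 1.4.

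The 16% and 68% follow from the AIC rule for a single one-parameter term and need no assumed effect size. The other results rest on the assumed odds ratios, variable types and correlations, and on the planned 220 patients and 30% remission. That intervals will be shown at 95% rests on the general rule in SAP 2.6.

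The primary non-inferiority conclusion is unaffected: it comes from the country-stratified Mantel-Haenszel risk difference with its 90% interval.

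**What to change.** In SAP 6.1, replace the selection rule with a sentence making the logistic model with all five pre-specified variables the main reported result, with every odds ratio and its 95% interval. If an AIC-reduced model is still wanted, show it after the full model and label it exploratory. State how autoantibody profile is coded, so that the number of parameters is fixed in advance.

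Country may be added as a fixed term because it is the randomisation stratum. This is optional: it goes beyond the protocol's list and lowers the events per parameter to about 9, or about 8 with a two-term autoantibody profile.

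The cost is SAP wording only, with no new data. The intervals will be somewhat wider than those the selected model would show.
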